#### **4.4.5. Pharmacokinetic Analysis Set**

The Pharmacokinetic (PK) Analysis Set will include all subjects who received investigational products with all evaluable PK data appropriate for the evaluation of interest (without major protocol deviations or violations that would have an impact on the absorption, distribution, metabolism, or excretion of investigational products). In other words, PK Analysis Set will include subjects who receive at least 1 dose of LC350189 and have sufficient concentration data to support accurate estimation of at least 1 PK parameter.

The PK analysis set will be used for analysis of PK endpoints, based on treatment that subjects received.

#### **4.5. Combination of Subjects in Analysis**

Data of subjects who have been randomized into the test (LC350189 50 mg, LC350189 100 mg, or LC350189 200 mg) or placebo groups before the implementation Protocol version 5.0 will be combined and analyzed with subjects who will be enrolled after the implementation of the Protocol version 5.0, as defined in protocol.

## 5. SUBJECT DISPOSITION

### 5.1. Disposition

The number of subjects screened, the number of subjects randomized, and the number of screen failures with the associated reasons for screen failure will be summarized.

Subject disposition (analysis set allocation, entered, discontinued, along with primary reason for discontinuation) will be summarized using frequency and percent for both treatment and follow-up phases based on the All Randomized Set.

Reasons for **End of Treatment or Early Termination**, as well as reasons for **Study Discontinuation** will be collected on the eCRF and will be summarized for all randomized subjects with the following categories:

- Adverse event
- Death
- Lack of efficacy
- Lost to follow-up
- Non-Compliance with Study Drug
- Physician Decision
- Pregnancy
- Progressive Disease
- Protocol Deviation/Violation
- Study Terminated by Sponsor
- Withdrawal by Subject
- Other

In addition, separate listings will be provided for:

- Screen failures
- Subjects excluded from analysis
- Discontinued subjects with reasons for treatment discontinuation

### 5.2. Protocol Deviations/Violations

The protocol deviations/violations will be identified and assessed by the clinical research physician or designee following company standard operational procedure and will be finalized prior to DBL.

The number and percentage of subject-level protocol deviations/violations will be summarized by dose cohort for the All Randomized Set, and a by dose cohort and by-subject listing in the All Randomized Set will be provided.

Site-level deviations will be listed.

## 6. DEMOGRAPHICS AND BASELINE CHARACTERISTICS

The demographics, baseline characteristics will be summarized for the Safety Analysis Set, the Full Analysis Set, and Per-Protocol Set.

Individual by-subject listings will be provided to support the summary tables.

### 6.1. Demographics

Subjects' age (years), height (cm), weight (kg), and Body Mass Index (BMI, kg/m^2) at baseline will be summarized using descriptive statistics; while sex, race, ethnicity, BMI categories ( $< 20 \text{ kg/m}^2$ ,  $20 \text{ to } < 25 \text{ kg/m}^2$ ,  $25 \text{ to } < 30 \text{ kg/m}^2$ ,  $\geq 30 \text{ kg/m}^2$ ), and other categorical variables will be provided using frequency tabulations.

### 6.2. Baseline Characteristics

The descriptive statistics for following variables will be presented:

- Smoking status at screening (Visit 1)
- Presence or absence of tophi at screening (Visit 1)
- Post-washout/pre-dose sUA ( $<9.8 \text{ mg/dL}$  or  $\geq 9.8 \text{ mg/dL}$ ) at baseline (Visit 3)
- Renal function at baseline (Visit 3)

### 6.3. Medical History and Concomitant Illness

Medical histories will be coded according to Medical Dictionary for Regulatory Activities (MedDRA, Version 21.0 or higher) and summarized based on the Safety Set by system organ class (SOC) and preferred term (PT).

Concomitant illness is any significant medical condition or disease that is present at study start (signing of informed consent). This includes clinically significant laboratory, ECG, or physical examination abnormalities noted at screening.

### 6.4. Physical Examination

The baseline physical examination will consist of the following body systems: (1) eyes; (2) ears, nose, throat, neck, thyroid; (3) cardiovascular system; (4) respiratory system; (5) gastrointestinal system, mouth; (6) dermatologic system; (7) extremities; (8) musculoskeletal system; (9) central and peripheral nervous system and (10) lymph nodes.

A summary of physical examination at baseline will be produced by body systems.

## 7. STUDY DRUG AND MEDICATIONS

### 7.1. Prior and Concomitant Medications

#### 7.1.1. Prior Medications

A prior medication is any medication that started before the first randomized study dose date, as Medication Start Date < Date of Study Day 1. In case of incomplete date, refer the methods specified in Section 14.3.2.

A summary showing the number and percentage of subjects who have prior medications will be presented by ATC level 2/level 4 and standardized medication name, using WHODD, for the Safety Set.

#### 7.1.2. Concomitant Medications

Concomitant medication is any medication given in addition to the investigational product(s), including over-the-counter medications, herbal medications, and vitamin supplements, that administered between screening and follow-up, as Medication End Date is on or after Study Day 1. In case of incomplete date, refer the methods specified in Section 14.3.2.

A medication will be categorized as “Prior/Concomitant” if it started before Study Day 1 and ended after Study Day 1. If a medication is taken on the Study Day 1, it will be counted as a concomitant medication.

Prior/Concomitant medications will be included in both summary for prior medications and summary for concomitant medications.

A summary showing the number and percentage of subjects who took concomitant medications will be presented by ATC level 2/level 4 and standardized medication name, using WHODD, for the Safety Set.

## 7.2. Study Drug

Summary and listing of study drug will be produced based on the Safety Set. Descriptive statistics for study drug compliance will be provided by treatment group.

### 7.2.1. Study Drug Dispense

On Day 1 (Visit 4), the appropriate study drug will be dispensed per the randomization code. Additional bottles will be dispensed on Day 28 (Visit 6) and Day 56 (Visit 7). At each of these three dispensing visits, subjects will receive a total of 2 bottles for LC350189/ placebo, and each bottle contains 35 capsules. On Day 28 (Visit 6), Day 56 (Visit 7), and Day 84 (Visit 8), all previously dispensed bottles should be returned for investigational product accountability.

### 7.2.2. Study Drug Compliance

Based on treatment group, study drug compliance will be measured at specific visits using the following formula:

| Treatment Group | Study Drug       |                  | Compliance (D) |
|-----------------|------------------|------------------|----------------|
|                 | Bottle 1         | Bottle 2         |                |
| LC350189 50 mg  | LC350189 25 mg   | LC350189 25 mg   | (B/2)/C*100%   |
| LC350189 100 mg | LC350189 100 mg  | LC350189 Placebo | B/C*100%       |
| LC350189 200 mg | LC350189 100 mg  | LC350189 100 mg  | (B/2)/C*100%   |
| Placebo         | LC350189 Placebo | LC350189 Placebo | (B/2)/C*100%   |

Where B is the total number of dispensed non-placebo capsules minus the total number of returned non-placebo capsules including lost or damaged ones (for Placebo group, placebo capsules of LC350189 will be considered), and C is the number of days since Day 1 for Day 28 (Visit 6); the number of days since Day 28 for Day 56 (Visit 7), and the number of days since Day 56 for Day 84 (Visit 8).

| Period             | Day when Accountability is Measured | Day when Bottles were Dispensed | B   | C (days)  |
|--------------------|-------------------------------------|---------------------------------|---|---|
| Visit 4 to Visit 6 | Day 28                              | Day 1                           | Sum of (35 minus the number of capsules left in each of bottle including lost or damaged ones)                              | (Date of Visit 6 – Date of First Dose of Study Treatment)   |
| Visit 6 to Visit 7 | Day 56                              | Day 28                          |   | (Date of Visit 7 – Date of Visit 6)   |
| Visit 7 to Visit 8 | Day 84                              | Day 56                          |   | (Date of Visit 8 – Date of Visit 7) *   |
| Overall            | Day of Last Dose                    | Day 1                           | Sum of (all dispensed non-placebo capsules) minus Sum of (all returned non-placebo capsules including lost or damaged ones) | (Date of Visit 8 – Date of First Dose of Study Treatment)
For early terminated subjects: (End of Treatment Date – Date of First Dose of Study Treatment + 1) |

\* Subjects will be guided not to administrate the study drug on Day 84. Even if the drug is administrated, it will be administrated after assessments. Therefore, Day 84 is exclusive to derivation of study drug compliance.

In case of early termination, the number of days of the last treatment period is derived as (Date of Last Dose of Study Treatment – Start Date of the Last Period +1).

### Study Drug Before the Implementation of Protocol Version 5.0

Subjects who are randomized before the implementation of Protocol Version 5.0 will continue receiving a total of 3 bottles for LC350189/febuxostat/placebo at each dispensing visit.

Based on treatment group, study drug compliance will be measured at specific visits using the following formula:

| Treatment Group | Study Drug       |                  |                    | Compliance (D) |
|-----------------|------------------|------------------|--------------------|----------------|
|                 | Bottle 1         | Bottle 2         | Bottle 3           |                |
| LC350189 50 mg  | LC350189 25 mg   | LC350189 25 mg   | Febuxostat Placebo | (B/2)/C*100%   |
| LC350189 100 mg | LC350189 100 mg  | LC350189 Placebo | Febuxostat Placebo | B/C*100%       |
| LC350189 200 mg | LC350189 100 mg  | LC350189 100 mg  | Febuxostat Placebo | (B/2)/C*100%   |
| Febuxostat      | LC350189 Placebo | LC350189 Placebo | Febuxostat         | B/C*100%       |
| Placebo         | LC350189 Placebo | LC350189 Placebo | Febuxostat Placebo | (B/2)/C*100%   |

Where B is the total number of dispensed non-placebo capsules minus the total number of returned non-placebo capsules including lost or damaged ones (for Placebo group, only placebo capsules of LC350189 will be considered), and C is the number of days since Day 1 for Day 28 (Visit 6); the number of days since Day 28 for Day 56 (Visit 7), and the number of days since Day 56 for Day 84 (Visit 8).

For each subject, the Overall study drug compliance is defined as the (sum of B)/(sum of C)\*100% throughout the treatment period.

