Subjects will be instructed to fast for at least 8 hours (preferably, overnight fast) prior to returning to the clinic on Day 14 (Visit 5), 28 (Visit 6), 56 (Visit 7), and 84 (Visit 8). On Day 14, 28, 56, and 84, subjects will withhold the investigational product until pre-dose laboratory samples have been obtained. Subjects will then take investigational product on site on Day 14 (Visit 5), 28 (Visit 6), and 56 (Visit 7), and blood samples will be obtained at the time points stated in the PK/PD sampling schedule (Section [9.1.14](#), [Table 9-3](#)). The last dose of investigational product that a subject will take is on Day 83. AEs will be recorded and measurements of laboratory parameters, vital signs, and 12-lead electrocardiogram (ECG) will be performed for safety evaluation according to the SOA ([Table 2-1](#)). Subjects will record the incidence of gout flares and rescue treatment using eDiary. Subjects will be assessed for the presence of tophi by palpation at the end of treatment visit (Visit 8). All tophi will be counted and recorded on the Tophi eCRF page.

Visit 9: Follow-up

A Follow-up on site-visit will be performed on Day 98 for safety assessments ([Table 2-1](#)).

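### The SAP's overall compliance formula for subjects randomized before Protocol version 5.0 omits the divisor of 2, so as written a full complier scores 200% in three arms

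*SAP*

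**What the plan says.** SAP 7.2.2 has two sets of compliance rules, one for subjects randomized under Protocol version 5.0 and one, under its own subheading, for those randomized before it.

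- **Before version 5.0, by period.** The arm table gives (B/2)/C × 100% for 50 mg, 200 mg and placebo, and B/C × 100% for 100 mg and febuxostat. The text below it states that "B is the total number of dispensed non-placebo capsules minus the total number of returned non-placebo capsules including lost or damaged ones". In the placebo arm the LC350189 placebo capsules are counted instead, and febuxostat placebo is left out.
- **Before version 5.0, overall.** The subsection closes with a sentence applying to each subject: "the Overall study drug compliance is defined as the (sum of B)/(sum of C"), times 100%. It has no divisor and makes no distinction by arm.
- **Version 5.0, overall.** The period table has an Overall row that restates only B and C. Its B is "Sum of (all dispensed non-placebo capsules) minus Sum of (all returned non-placebo capsules including lost or damaged ones"). It gives no complete formula, so the divisor in the arm table above it can still apply.

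On use, SAP 7.2 says: "Descriptive statistics for study drug compliance will be provided by treatment group". SAP 4.5 says that LC350189 and placebo subjects randomized before version 5.0 "will be combined and analyzed with subjects who will be enrolled after the implementation of the Protocol version 5.0".

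**The concern.** The divisor of 2 is there because two counted capsules make up one daily dose in the 50 mg, 200 mg and placebo arms. Summing B and C over the three periods does not remove the need for it. A formula that drops it doubles overall compliance in those arms and leaves the 100 mg and febuxostat arms correct.

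This is not a harmless change of scale, for three reasons:

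- Overall compliance would not be comparable between arms.
- It would contradict the same subject's period values.
- It would hide poor adherence, since a subject taking half the doses would appear fully compliant.

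Because earlier and later subjects are pooled within an arm, one arm's summary could also mix two scales.

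**Working it through.** The SAP states a formula here and no numerical result, so there is no printed figure to reproduce. The check applies the formulas to a known pattern of use.

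**Inputs**

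- Dosing days: Protocol 6.2 states "The last dose of investigational product that a subject will take is on Day 83", and SAP 7.2.2 adds "Therefore, Day 84 is exclusive to derivation of study drug compliance".
- C by period: 28 − 1 = 27, 56 − 28 = 28 and 84 − 56 = 28, so the sum of C is 83.
- Counted capsules per day: two in the 50 mg, 200 mg and placebo arms and one in the 100 mg arm (Protocol 8.4 and the SAP 7.2.2 arm tables); one in the febuxostat arm (the SAP arm table before version 5.0).
- Bottle size: SAP 7.2.1 says "and each bottle contains 35 capsules", with dispensing on Days 1, 28 and 56.

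**Full complier in the 50 mg, 200 mg or placebo arm**

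- B = 54, 56 and 56, sum 166.
- By period: (54/2)/27, (56/2)/28 and (56/2)/28, each 100%.
- Overall as written: 166/83 = 200%.
- Overall with the arm divisor: (166/2)/83 = 100%.

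**Full complier in the 100 mg or febuxostat arm**

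- B = 27, 28 and 28, sum 83.
- Each period is 100%, and overall is 83/83 = 100%.

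**Partial adherence**, the same share of doses taken in every period:

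| Share taken | Each period, any arm | Overall as written: 50 mg, 200 mg, placebo | Overall as written: 100 mg, febuxostat |
|---|---|---|---|
| 100% | 100% | 200% | 100% |
| 80% | 80% | 160% | 80% |
| 60% | 60% | 120% | 60% |
| 50% | 50% | 100% | 50% |
| 40% | 40% | 80% | 40% |

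With the divisor restored, the overall value equals the period value in every row and every arm.

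**Robustness.** The factor does not depend on visit timing: with two capsules a day over d days, the sum of 2d divided by the sum of d is always 2. Moving Visits 6 and 8 by 2 days either way leaves 200% unchanged, as does stopping after 40 days (80/40).

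**Is 200% a possible value?** Three dispensings of 35 give 105 capsules per bottle position. The highest true overall compliance is (210/2)/83 = 105/83 = 126.5%; the literal rule would give 210/83 = 253.0%. This assumes the 35-capsule bottle was also used before version 5.0.

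**Effect after pooling.** Let f be the share of an arm randomized before version 5.0, which the documents do not give. If all subjects comply fully and the sentence covers only the earlier subjects, the pooled mean in the three arms is 100(1 − f) + 200f = 100(1 + f)%, anywhere from 100% to 200%. If the sentence is read as covering all subjects, it is 200% at any f.

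**The case against.** The strongest reply is that this is a slip in one sentence and that the divisor is implied. The Overall row for version 5.0 prints no divisor either, and the earlier subsection has the same kind of arm table just above its closing sentence, so that sentence could be read as saying only how to add up B and C. The divisor probably was intended. But the sentence writes out a complete formula, including the multiplication by 100%, whereas the Overall row gives only the two components. Nor can B be taken as already halved, because the table above divides the same B by 2. A programmer or validator following the text would get 200%.

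The second reply concerns reach, and most of it stands:

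- SAP 4.4.4 leaves the overall compliance algorithm and the per-protocol cutoff to a blinded data review meeting before database lock, so this sentence does not bind the per-protocol set.
- The 80% and 120% limits in Protocol 8.4.1 apply to the period since the last visit, and the SAP's period formulas are correct.
- Group values near 200% would probably be noticed at table review. A single half-complier scoring 100% is harder to spot, although the period values would show about 50%.

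Third, the rules for C at early termination are not identical. The version 5.0 Overall row uses the end-of-treatment date, while the rule for the last period uses the date of last dose. The two agree only when those dates coincide. This is true, but it concerns C and does not bear on the missing divisor.

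**Conclusion.** The concern holds. As written, the overall rule for subjects randomized before version 5.0 doubles compliance in the 50 mg, 200 mg and placebo arms and is correct in the 100 mg and febuxostat arms. The factor of exactly 2 follows from the SAP's own definitions at any level of adherence. Only the supply ceiling and the pooled mean rest on assumptions: the bottle size before version 5.0 for the first, and full compliance with an unknown f for the second.

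The consequence is limited. A planned descriptive summary would be wrong in three arms and not comparable across arms. The primary analysis on the full analysis set is unaffected, and the supportive per-protocol analysis is affected only if the data review meeting takes up this formula. It should be corrected because the error is certain and the correction is trivial.

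**What to change.** Replace the closing sentence of the subsection on subjects randomized before version 5.0 with an arm-specific rule:

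- 50 mg, 200 mg and placebo: overall compliance = ((sum of B)/2)/(sum of C) × 100%.
- 100 mg and febuxostat: overall compliance = (sum of B)/(sum of C) × 100%.

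This gives 100% for a full complier in all five arms and, for completers, agrees with the version 5.0 Overall row once its arm divisor is applied. A cross-reference to that row, keeping the subsection's own arm table and definition of B, would do the same job and would also settle which end date is used for early terminators.

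The cost is one SAP sentence, with no new data and no change to any efficacy analysis.

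A separate and lesser point is that Protocol 8.4.1 does not say whether its own formula is per bottle or for all capsules. It would be worth clarifying this and reconciling it with the SAP. That would be a protocol edit, and the SAP correction need not wait for it. No change to the protocol's compliance limits is proposed.

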#### 7.2.3. Actual Dosage of LC350189

Actual dosage of LC350189 of a subject is calculated as:

Actual dosage = Sum of (dosage of capsules with active ingredient)/Sum of (dosing days)

Example: Subject C was randomized to LC350189 200 mg but took 2 bottles of LC350189 25 mg daily for 28 days, then the actual dosage is LC350189 50 mg.

In Safety Analysis, subjects will be summarized by treatment received.

#### 7.2.4. Subjects Who Ever Took Unassigned Dose

In practice, a subject may receive and take LC350189 capsules with unassigned doses therefore actual dosage may be different from pre-defined study doses (LC350189 50 mg, 100 mg, or 200 mg). In that case, subjects will be summarized in the most frequently applied dose level and the “LC350189 All” column in Safety tables. If the most frequently applied dose level is not in the pre-defined doses, the subject will be summarized only in the “LC350189 All” column.

Examples: Assuming a subject was assigned to 50 mg group. 1) If this subject took proper doses during the majority of the treatment period and a few 200 mg doses by chance, this subject will be categorized in 50 mg group; 2) If this subject took 200 mg doses during the majority of the treatment period and a few 50 mg doses, this subject will be categorized in 200 mg group; 3) If

for some reasons this subject took 150 mg doses for the entire treatment period, this subject will be not categorized into any pre-defined doses, and summarized only in the “LC350189 All” column.

In Safety Analysis, 1) subjects in Febuxostat group took both active Febuxostat and its placebo will be summarized in “Febuxostat” column, 2) subjects in Placebo group took both active Febuxostat and its placebo will be summarized in “Febuxostat” column, 3) subjects in Febuxostat group took only Febuxostat placebo will be summarized in “Placebo” column, and 4) subjects who took both active Febuxostat and active LC(50mg, 100mg, or 200mg) dose will be summarized in the most frequently applied dose group..

Subjects who ever took unassigned dose will be excluded from PPS, unless the unassigned doses taken were administered for the entire treatment duration.

### **7.3. Gout Flare Prophylaxis**

Gout flare prophylaxis will consist of colchicine 0.6 mg (QD) starting at Visit 2 (between Day -30 to Day -23) through the end of the treatment period.

Summary and listing of gout flare prophylaxis will be produced, by treatment group.

## 8. EFFICACY ANALYSIS

Efficacy analysis will be conducted using FAS and PPS.

For subjects randomized into the active control group (febuxostat) before the implementation of the Protocol version 5.0, efficacy data (sUA and anti-flare activities) and exploratory data (HbA1c, FPG, and hs-CRP) will be only listed.

### 8.1. Analysis of Efficacy Endpoints

The efficacy endpoints of this study are specified in Sections [3.2.1](#), [3.2.2](#), and [3.2.4](#) of this SAP.

All endpoints will be summarized descriptively and will be compared to placebo using descriptive statistics.

Proportions will be analyzed using the Cochran-Mantel Haenszel (CMH) test adjusted by following stratification factors: 1) tophi status at Visit 1, and 2) sUA (level <9.8 mg/dL or  $\geq 9.8$  mg/dL) at Visit 4. The Wald asymptotic 95% confidence limit will be calculated for the risk difference point estimate for pairwise comparisons between each dose group and placebo in pre-specified order of 200 mg versus placebo, 100 mg versus placebo and 50 mg versus placebo; however, if the data suggest and warrant it, the continuity correction adjusting for the difference between the normal approximation and the binomial distribution will be applied. Subgroup analyses of proportions of subjects with sUA level < 5.0 mg/dL (and 6.0 mg/dL as well) will be performed by above stratification factors.

Change and percent change from baseline will be analyzed with an analysis of covariance (ANCOVA) model, including treatment, sUA and tophi strata at screening, and baseline values of the dependent variable as a covariate.

As this is not a rigorous confirmatory trial, no multiplicity adjustment is planned for multiple treatment comparisons or multiple endpoints.

Dropouts will be treated according to non-responder imputation (NRI).

